## Protocol synopsis

Name	PREG1
Title	PRE vention of intrauterine adhesion after hysteroscopic surgery with novel tri-block de G radable polymer film
Protocol version number	06 (April 27th 2020)
Study rationale	Intrauterine adhesions (IUA) are defined as “fibrous strings at opposing walls of the uterus and/or cervix leading to partial or complete obliteration of the cavity”  . IUAs are the major long-term complication of operative hysteroscopy. Their prevalence following myomectomy is high and varies significantly across the literature (7.5%-45.5%)  . They are frequently associated with pelvic pain. The prevention tools available today do not sufficiently meet the specifications required for the prevention of IUAs which are: 1) ergonomic device, specifically designed for intrauterine use and adapted to the cervical passage and 2) anti-adhesion barrier that keep the wound tissue apart during the repair phase for optimal efficiency.
Study device	
Name: Womed Leaf  Device group: Anti-adhesion barrier  Device status: CE marked  Classification (according to MDD 93/42/EEC as amended per 2007/47/EC): IIa according to rule 5
 
Intended purpose:  Womed LeafTM is a sterile, degradable film of poly(D,L-lactide) (PLA) and poly(ethylene oxide) (PEO). PEO is a biocompatible polymer with anti-adhesion and swelling properties. Polymerized with hydrophobic PLA, it forms a degradable film that swells and expands in contact with water to form a degradable mechanical barrier.
 
Womed LeafTM is inserted in the uterine cavity by a gynecologist surgeon as a film folded into a 5 mm diameter

 Hooker et al. Prevalence of intrauterine adhesions after the application of hyaluronic acid gel after dilatation and curettage in women with at least one previous curettage: short-term outcomes of a multicenter, prospective randomized controlled trial, *Fertility and Sterility*, 2017;107:1223-31

 Taskin et al. Role of endometrial suppression on the frequency of intrauterine adhesions after resectoscopic surgery. *The Journal of the American Association of Gynecologic Laparoscopists* 2000;7(3):351-4

 Guida et al. Effectiveness of auto-crosslinked hyaluronic acid gel in the prevention of intrauterine adhesions after hysteroscopic surgery: a prospective, randomized, controlled study. *Human Reproduction* 2004;19(6):1461-64

 Touboul et al. Uterine synechiae after bipolar hysteroscopic resection of submucosal myomas in patients with infertility. *Fertility and Sterility* 2009;92(5):1690-93

	flexible inserter. Once released, the film will unfold and swell into the uterine cavity to keep uterus walls separated during approximately 5 days. It is degraded and discharged naturally through the cervix and vagina in less than 30 days.
Intended use	Womed Leaf™ is intended to be used for the prevention or reduction of new or recurrent intrauterine adhesion formation subsequent to a transcervical procedure by creating a mechanical barrier.
Design	Prospective, multi-center, single arm clinical study. Subjects will be followed up for 4 to 8 weeks.
Objective	Evaluate the safety of Womed Leaf after hysteroscopic myomectomy and its potential efficacy in preventing IUA at second look hysteroscopy.
Number of subjects	20 subjects
Sites	
 
● Kremlin Bicêtre (APHP), Paris, France,
 
● CHU Nîmes, France,
 
● AMC, Amsterdam, The Netherlands
 
● Zaans, The Netherlands
 
● Isala, Zwolle, The Netherlands
 
● Gent, Belgium
 
● CHR La Citadelle, Liège, Belgium
 

Population	Women with one or more myoma(s), one myoma being larger than 10mm, who qualify for hysteroscopic myomectomy
Co-primary endpoints	
 
● Safety endpoint: number and type of device-related adverse events (AE) up to 30 days: 
 
○ Per-operative AEs during device use (cervical trauma, uterine perforation...)
 
○ Polymer film tolerance defined as fever, pain or bleeding between 48 hours post procedure and 30 days
 
 
 
 
An Interim Analysis of the safety endpoint will be conducted on the first 10 subjects at 30 day follow-up.
 
 
● Efficacy endpoint: freedom from intrauterine adhesion at second look hysteroscopy between 4 and 8 weeks, and evaluation of severity according to American Fertility Society (AFS) and European Society of Gynecological Endoscopy classifications systems of adhesions.
 

Secondary endpoints	
 
1. Number, type and severity of adverse events (AE) at 30 days
 
2. Performance: device technical success, defined as success of the following 2 steps :
 

	
 
a. Insertion of the inserter into the cervix with loaded film
 
b. Release of the film in the uterus defined as empty inserter after withdrawal
 
 
 
3. Menstrual bleeding according to Higham score
 
4. Presence of Womed Leaf residuals in the uterus at hysteroscopic control
 
5. Uterine film discharge experience as recalled by subject at second look hysteroscopy visit : 
 
a. Subject estimation of film discharge timing and duration.
 
b. Vulvar pruritus or other discomfort
 
c. Qualitative impression
 
 
 
6. Device manipulation duration, from insertion to withdrawal
 

Inclusion criteria	
 
1. Women <math>\geq 40</math> years AND no childbearing wish, OR history of permanent sterilization
 
2. Subject scheduled for myomectomy for one or more myoma(s) where one myoma is at least 10mm in size (<math>\geq 10</math>mm) as estimated by pre-operative ultrasound measurement of the largest diameter
 
3. Hysterometry <math>\geq 6</math> cm and <math>\leq 9</math> cm as measured prior to device insertion
 
4. Subjects who are willing to provide a written informed consent as approved by the applicable Ethics Committee prior to participating in this clinical investigation.
 
5. Subjects who can comply with the study follow-up or other study requirements
 

Exclusion criteria	
 
1. Current pregnancy
 
2. Abnormal uterine cavity according to ESHRE classification I to VI, such as unicornis, bicornis, septate, duplex
 
3. Known or suspected endometrial hyperplasia
 
4. Medical history of cervical or endometrial cancer
 
5. Active pelvic infection or medical history of pelvic peritonitis
 
6. Intrauterine device in situ
 
7. Known contraindication or hypersensitivity to Womed Leaf components and to medications such as aspirin;
 
8. Concurrent medical condition with a life expectancy of less than 12 months;
 
9. Full endometrial ablation
 

	
Per-operative exclusion criteria:
 
 
10. Adenomyosis
 
11. Inflammation (endometritis)
 
12. Abnormal uterine cavity, including IUA
 
13. Hysterometry < 6cm or >9cm
 
14. Any complication during the intervention that is deemed to potentially interfere with the objective of the study by the investigator
 

Intervention technique	
 
● No monopolar energy
 
● Resection is limited to myoma and excludes full endometrial ablation
 

Drug regimen	According to local practice of the participating site
Assessment / Data and image collection / Follow up schedule	
 
● Intervention: recording of hysteroscopy procedures and 2D or 3D US imaging
 
● 2 hours after the procedure (i.e.before discharge): 2D or 3D ultrasound in order to visualize the polymer position and swelling in the uterine cavity.
 
● All subjects will be contacted at 30 days post procedure to assess their clinical status and adverse events.
 
● All subjects will undergo “second look” hysteroscopic procedure between 4 to 8 weeks. Recording of hysteroscopy images.
 

Timelines	First subject will be included in S2 2019. Enrollment of the 20 subjects will last 12 months. Study is expected to be closed by Q4 2020.
Statistical Analysis Plan	Descriptive statistics will be provided for all variables considered in the analysis. For categorical variables, the data will be presented as counts and incidence rates. For continuous variables, the data will be presented as mean, standard deviation, median, minimum, maximum and number of observations.
Applicable Norms	ISO 14155

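### Film discharge is asked about at the second look (day 28 to 56) rather than at the existing day-30 contact, so recall is uneven and, for visits after day 30, longer than needed

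*Protocol*

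**What the plan says.** All references are to the Protocol synopsis.

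- **Secondary endpoints, item 5** is headed "Uterine film discharge experience as recalled by subject at second look hysteroscopy visit". Its parts are "Subject estimation of film discharge timing and duration", pruritus or other discomfort, and a qualitative impression.
- **Assessment and follow-up schedule** places the second look hysteroscopic "procedure between 4 to 8 weeks". It also states: "All subjects will be contacted at 30 days post procedure to assess their clinical status and adverse events".
- **Study device** says that the film will "keep uterus walls separated during approximately 5 days". On its removal from the body it says: "It is degraded and discharged naturally through the cervix and vagina in less than 30 days".
- **Secondary endpoints, item 4** records "Presence of Womed Leaf residuals in the uterus at hysteroscopic control".
- **Statistical Analysis Plan** row: "Descriptive statistics will be provided for all variables considered in the analysis".

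The synopsis mentions no diary and no question on discharge before the second look.

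**The concern.** By the device description, the event that item 5 asks about should be over by day 30. A contact with every subject exists at that time. The endpoint definition nevertheless ties the questions to a visit that can come up to 26 days later and has a window of four weeks. The time between the event and the question then depends on when the visit was booked as well as on when the film left.

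Item 5 is the only listed endpoint that dates the discharge. Item 4 shows whether film is present on the day of the look. For a woman seen after day 30, an empty cavity does not show that the film left within 30 days. The subject's own estimate is therefore the listed information that bears on the stated discharge time, and in a 20-subject study a few poorly dated answers are visible in the reported mean, standard deviation and range. Mild discomfort that nobody reports as an adverse event is also easier to forget when the targeted question comes late.

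The time of questioning is part of the endpoint's wording, so this is a choice that the protocol makes, not a detail left to a separate analysis plan.

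**Working it through.** The plan gives no figure to reproduce here, and no sample size or power calculation is involved. The check is date arithmetic.

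**Inputs**
- Second look: 4 × 7 = day 28 to 8 × 7 = day 56, counted from the procedure (Assessment and follow-up schedule).
- Existing contact: day 30, all subjects (same row). The synopsis gives no window for it, so day 30 is taken as exact.
- Discharge complete before day 30, so day 29 at the latest (Study device).
- Earliest discharge: day 5. This is an assumption, taken from the period of about 5 days during which the film separates the walls. The other discharge days below are also assumed, to show the range.

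**Window**
- Width: 56 − 28 = 28 days.
- Possible visit days: 56 − 28 + 1 = 29. Those after day 30: 56 − 30 = 26. Share: 26 / 29 = 0.897. This counts calendar days and does not predict how visits will be booked.

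**Recall lag** = day of questioning − day of discharge

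| Discharge day | Lag if asked on day 30 | Lag at second look (day 28 to day 56) |
|---|---|---|
| 5 | 25 | 23 to 51 |
| 10 | 20 | 18 to 46 |
| 15 | 15 | 13 to 41 |
| 20 | 10 | 8 to 36 |
| 25 | 5 | 3 to 31 |
| 29 | 1 | −1 to 27 |

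The negative value means that on day 28 the discharge has not yet happened.

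**Excess over a day-30 question** = visit day − 30, whatever the discharge day: from 28 − 30 = −2 to 56 − 30 = +26 days. For discharge on day 10, a day-56 visit gives 46 / 20 = 2.3 times the day-30 lag. If visits were spread evenly over the window (assumption), the mean visit day would be 42, which is 42 − 30 = 12 days later than the contact.

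**Spread between women with the same discharge day**: up to 56 − 28 = 28 days as written.

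**With questioning at whichever of the two comes first**: the first question falls between day 28 and day 30, so the spread caused by visit date is at most 30 − 28 = 2 days. A woman seen on day 28 whose film leaves on day 29 is picked up at the day-30 contact, with a lag of 1 day.

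**The case against.** The case for leaving the item alone is reasonable. Item 5 is openly labelled as recall and as the subject's estimate. It is secondary and descriptive in a 20-subject single-arm study, and no threshold or decision depends on it. For most of the window the second look falls after the expected end of discharge, so one interview covers the whole episode and sits beside the hysteroscopic finding. All of this stands and sets the priority, but it does not explain why a contact that already exists at the right time goes unused for these questions.

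A reader might infer more than the documents support:

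- *That recall is longer for everyone.* It is not. On day 30 it is equal, and on days 28 and 29 it is shorter by 2 and 1 days.
- *That discomfort is lost from the safety data.* Adverse events are collected at day 30 and feed both the co-primary safety endpoint and secondary endpoint 1. Discomfort reported as an adverse event is therefore captured then. Only milder discomfort, timing, duration and impression rest on item 5.
- *That item 5 is the only evidence on clearance of the film.* Item 4 is a direct observation for each subject, though it does not date the discharge.
- *That the discharge figures will be biased by a known amount.* Days of delay are not recall error. Nothing in the documents links the two, and no bias is estimated here.

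Fuller protocol sections or case report forms, which are not available, may contain a diary. Its use would still not match the endpoint as worded.

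**Conclusion.** The point holds as a minor one. As written, item 5 takes discharge timing, duration and discomfort at a visit that makes recall up to 26 days longer than a day-30 question would need, on 26 of the 29 possible visit days. It also lets recall time differ by up to 28 days between women with the same discharge day. Visits on days 28 to 30 have no longer recall, but on days 28 and 29 the discharge may be incomplete by the plan's own description.

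The 26-day and 28-day figures do not depend on the assumed discharge days, provided that discharge precedes the questioning. They do rest on the second look window being counted from the procedure and on the contact taking place on day 30. If that contact drifts, the gain shrinks accordingly. The consequence is limited to the precision and comparability of one descriptive secondary endpoint; the co-primary endpoints are unaffected.

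**What to change.** Reword the lead of secondary endpoint 5 along these lines:

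> Film discharge experience as reported by the subject at the 30-day contact or at the second look, whichever comes first, with any discharge or discomfort occurring after that first questioning added at the later of the two.

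The whichever-comes-first rule is needed because a second look on day 28 or 29 precedes the contact. A rule that used the second look only for events after day 30 would have no meaning for those women.

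The cost is a few extra questions at a contact that already takes place, with no new visit or procedure. For some subjects the account will be combined from two interviews, so the date of each should be recorded with the answers. Version 06 is dated April 2020 and first inclusion was planned for the second half of 2019. Some subjects may therefore have finished already, and the change would apply to those still to reach day 30.

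### Does presenting freedom from adhesion as a count and rate, with no confidence interval named, leave the co-primary efficacy result open to over-reading?

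*Protocol*

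**What the plan says.** All the relevant text is in the protocol synopsis. The Design row describes a "Prospective, multi-center, single arm clinical study", and the Number of subjects row gives 20. The Objective row puts safety first and adds "its potential efficacy in preventing IUA at second look hysteroscopy". The Co-primary endpoints row defines the efficacy endpoint as "freedom from intrauterine adhesion at second look hysteroscopy between 4 and 8 weeks", together with a grading of severity.

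The Statistical Analysis Plan row has three sentences. The first sets the scope: "Descriptive statistics will be provided for all variables considered in the analysis". The second covers categorical data: "For categorical variables, the data will be presented as counts and incidence rates". The third lists, for continuous data, "mean, standard deviation, median, minimum, maximum and number of observations". The row names no endpoint, no interval, no test and no confidence level.

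The Study rationale row cites a prevalence of adhesions after myomectomy of 7.5% to 45.5%, as background.

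**The concern.** Freedom from adhesion is a yes/no outcome, so the categorical rule covers it. Read as a complete list of outputs, the row would have the main efficacy result of an uncontrolled study of 20 women reported with no measure of precision. Continuous variables at least get a standard deviation and a range.

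There is no control arm, so readers will set the observed rate beside the cited 7.5% to 45.5%. A result such as 20 of 20 free of adhesion looks decisive when stated bare, yet it could arise fairly often without any device effect if the background rate were at the low end of that range. What seems to be at stake is an efficacy impression stronger than 20 subjects can support.

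**Working it through.** **Is there a plan figure to reproduce?** No. The 20 subjects are stated without an expected rate, reference rate, error level, power or target precision. The check is therefore how imprecise the proportion is, and then whether the protocol's wording leads to a wrong result.

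**Inputs.** n = 20 (Number of subjects row); background rates 7.5% and 45.5% (Study rationale row). The two-sided 95% level, the outcomes x and the 18-subject case are assumptions.

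**Step 1: precision of x/20, exact (Clopper-Pearson).** For x = n the lower limit is 0.025^(1/n). With n = 20, 0.025^(1/20) = 0.832. For other x the limits are the beta quantiles B(0.025; x, n−x+1) and B(0.975; x+1, n−x).

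| Free of adhesion | Rate | Exact 95% interval |
|---|---|---|
| 20/20 | 100% | 83.2% to 100% |
| 18/20 | 90% | 68.3% to 98.8% |
| 16/20 | 80% | 56.3% to 94.3% |

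If only 18 women had a second look, 18/18 would give 81.5% to 100% and 16/18 would give 65.3% to 98.6%.

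**Step 2: chance of a high rate with no device effect.** At a true adhesion rate of 7.5%, P(20/20) = 0.925^20 = 0.21 and P(at least 18/20) = 0.81. At 45.5%, P(at least 18/20) = 0.0008. The imprecision is therefore real and, at the low end of the range, large.

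**Step 3: does the prescribed output hide it?** The row asks for the count as well as the rate, and the two together return the denominator: 20 with 100% gives 20/1.00 = 20; 18 with 90% gives 18/0.90 = 20; 16 with 88.9% gives 16/0.889 = 18. Every interval in Step 1 can be computed from the reported figures.

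**Step 4: does the row exclude an interval?** It contains no word of limitation. It applies the same summaries to every variable and sets no endpoint-specific analysis. A statistical analysis plan that added an exact interval for freedom from adhesion would not contradict it.

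**Step 5: does any planned conclusion depend on an interval?** The synopsis states no hypothesis, success criterion, comparison with the cited prevalence or claim of proven efficacy. It is true that no result in 20 subjects puts the upper limit for adhesions below 7.5%: with none observed the limit is 1 − 0.832 = 16.8%, and getting below 7.5% would take 48 subjects (1 − 0.025^(1/48) = 7.40%; 47 subjects give 7.55%). But the study does not set out to exclude 7.5%, so this exposes no failure of the plan.

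**The case for a change.** The strongest opposing argument is that the protocol does more than stay silent: it states how categorical results will be presented, and a co-primary proportion falls within that statement. An interval needs no hypothesis, so it suits a descriptive study. It costs one sentence, and naming the method in advance prevents a choice after the data are seen. That readers could work it out themselves is a weak reason not to print it.

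Much of this stands as advice on reporting. An exact interval beside the proportion would be good practice, and the limits above show it would be informative.

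It does not make the row wrong. The argument needs the row to be a closed list, and the text does not say so. The level and method of an interval are ordinary content of a statistical analysis plan, and the point would disappear if that document specifies one. Nor would an interval remove the main limit on interpretation, which is the absence of a control arm; the Design row states that openly.

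**Conclusion.** The concern does not hold. A single proportion in 20 subjects is imprecise, with exact 95% intervals about 17 percentage points wide at 20/20, 30 at 18/20 and 38 at 16/20. But the protocol neither misstates nor conceals this. Followed as written, it yields a correct count and rate with a recoverable denominator, in a descriptive single-arm study whose efficacy aim is cautiously worded and tied to no test or threshold. The absence of a named interval is a detail commonly left to the statistical analysis plan.

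This conclusion rests on two readings: that the Statistical Analysis Plan row is a summary and not an exhaustive list, and that no efficacy claim or benchmark is set elsewhere. The document at hand supports both. A statement that intervals will not be given, or a success criterion based on the bare rate, would reopen the question; the protocol contains neither.
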